9.1.3 Visit 2: Operation through Discharge Visit

- Query subject regarding any changes in general health and the use of concomitant medications
- If any adverse device effects or device deficiencies are observed or reported, they must be recorded as instructed in Section 12.3 adverse events and device deficiencies
- Update information in the Screening and Enrollment Log
- Intra-operative success as assessed by the surgeon
- MRI/Images, only in case of repair failure
- Complete Operation and Discharge Visit CRFs
- Instruct the subject on follow-up procedures, including returning to the facility for FU Visit 3 in (\pm 1M) 6 months

9.1.4 Visit 3: 6-Month Follow-up Visit (\pm 1 month)

- Query subject regarding any changes in general health and the use of concomitant medications.
- If any adverse device effects or device deficiencies are observed or reported, they must be recorded as instructed in Section 12.3, adverse events and device deficiencies
- Post-operative repair failure
- Complete VAS-Scale for Pain and Satisfaction for all subjects*
- Complete EQ-5D questionnaire for all subjects*
- Complete ROWE Score for shoulder*
- ASES Score for shoulder*
- Complete Constant-Murley Score for shoulder*
- Complete HOOS-ADE Score for hip*

Study Protocol—Device	
Prospective, Multicenter, Post-Market Clinical Follow-up Study to evaluate safety and performance of the SUTUREFIX ULTRA and SUTUREFIX CURVED Suture Anchors in shoulder and hip arthroscopic repair	Number: 17-5010-06
	Version: 1.0, 09/MAY/2018
	Page: Page 41 of 87

- Complete Modified HSS Sore for hip*
- Perform MRI/Imaging only in case of repair failure
- Complete 6-Months Follow-up Visit CRFs
- Instruct the subject on follow-up procedures, including scheduling a FU call or visit in (\pm 1M) 12 months

**Patient Reported Outcomes (PROs) are optional and used according to the surgeon's preference.*

9.1.5 Visit 4: 12-Months Follow-up Call or Visit (\pm 1 month)

- Query subject regarding any changes in general health and the use of concomitant medications.
- If any adverse device effects or device deficiencies are observed or reported, they must be recorded as instructed in Section 12.3, adverse events and device deficiencies.
- Post-operative repair failure
- Complete VAS-Scale for Pain and Satisfaction for all subjects*
- Complete EQ-5D questionnaire for all subjects*
- Complete ROWE Score for shoulder*
- ASES Score for shoulder*
- Complete Constant-Murley Score for shoulder*
- Complete HOOS-ADE Score for hip*
- Complete Modified HSS Sore for hip*
- Perform MRI/Imaging only in case of repair failure

**Patient Reported Outcomes (PROs) are optional and used according to the surgeon's preference.*

Study Protocol—Device	 smith&nephew
Prospective, Multicenter, Post-Market Clinical Follow-up Study to evaluate safety and performance of the SUTUREFIX ULTRA and SUTUREFIX CURVED Suture Anchors in shoulder and hip arthroscopic repair	Number: 17-5010-06
	Version: 1.0, 09/MAY/2018
	Page: Page 42 of 87

9.1.6 Unscheduled Visits

- Query subject regarding any changes in general health and the use of concomitant medications.
- Adverse device effects or device deficiencies must be recorded as instructed in Section 12.3, adverse events and device deficiencies.
 - Post-operative repair failure
- Complete VAS-Scale for Pain and Satisfaction for all subjects*
- Complete EQ-5D questionnaire for all subjects*
- Complete ROWE Score for shoulder*
- ASES Score for shoulder*
- Complete Constant-Murley Score for shoulder*
- Complete HOOS-ADE Score for hip*
- Complete Modified HSS Score for hip*
- Perform MRI/Imaging to investigate repair failure
- Complete Unscheduled Visit CRFs

**Patient Reported Outcomes (PROs) are optional and used according to the surgeon's preference*

Unscheduled examinations may be conducted at the discretion of the Investigator with all obtained information recorded in the source documents and on the appropriate CRF.

9.1.7 Concomitant Medications and Therapies

A concomitant medication (e.g. drug, substance) and a concomitant therapy (e.g. physical therapy, TENS Unit, massage) are recorded at any time from enrollment into the study through the subject's last study visit.

Study Protocol—Device	
Prospective, Multicenter, Post-Market Clinical Follow-up Study to evaluate safety and performance of the SUTUREFIX ULTRA and SUTUREFIX CURVED Suture Anchors in shoulder and hip arthroscopic repair	Number: 17-5010-06
	Version: 1.0, 09/MAY/2018
	Page: Page 43 of 87

9.1.7.1 *Concomitant Medications*

9.1.7.1.1 Excluded Concomitant Medications

Not applicable

9.1.7.1.2 Recording Concomitant Medications in the CRF

Concomitant medications should be recorded in the CRF with the generic name.

9.1.7.2 *Concomitant Therapies*

9.1.7.2.1 Therapies Prohibited During the Study

Not applicable

9.1.7.2.2 Recording Concomitant Therapies in the CRF

Standard concomitant therapy will be recorded in the CRF unless provided as a part of an AE treatment.

9.1.8 Discontinued Subjects

Discontinued subjects are those who voluntarily discontinue participation, who are withdrawn for reasons of safety, who are lost to follow-up, so are ineligible for further participation, refer to section 7.8 for further details. Where possible, a full Exit Visit should be completed for all subjects who discontinue the study early. Where consent is withdrawn, the date and any reason given for discontinuation should be captured, at a minimum (see Section 7.8.2).

Finally, if appropriate, the Investigator will also advise the subject of subsequent therapy and/or procedures necessary for their medical condition.

Study Protocol—Device	
Prospective, Multicenter, Post-Market Clinical Follow-up Study to evaluate safety and performance of the SUTUREFIX ULTRA and SUTUREFIX CURVED Suture Anchors in shoulder and hip arthroscopic repair	Number: 17-5010-06
	Version: 1.0, 09/MAY/2018
	Page: Page 44 of 87

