7.7 LOST TO FOLLOW-UP

Some actively enrolled subjects will not return for follow-up exams on time. Study personnel must make a reasonable effort to contact the subject and document the following contact attempts prior to declaring a subject to be lost to follow-up: the subject has been contacted according to the site's policies, but no fewer than 2 documented phone contacts and 1 certified letter without response. Copies of all attempts to reach the subjects per regular mail or email and/or the attempts to contact the subject via other means should be documented and that documentation should be kept with the subject's source documents.

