7.8.2 Withdrawal from Study

The Investigator **may** withdraw subjects from the study for many reasons, including but not limited to the following:

- subject noncompliance (e.g. did not follow instructions)
- subject lost to follow-up
- if the Investigator or the Sponsor stops the study for any reason and decides to withdraw subject(s) from the study
- Adverse Events/

Suturefix Ultra Suture Anchor	
Suturefix Curved Suture Anchor	
Prospective, Multicenter, Post-Market 1 year Clinical Follow-up Study to evaluate safety and performance of the SUTUREFIX ULTRA and SUTUREFIX CURVED Suture Anchors in shoulder and hip arthroscopic repair	Number: 17-5010-06
	Version: 1.0, 09/MAY/2018
	Page: Page 33 of 87

- any other significant reason identified by the Investigator

For each case, information will be obtained in the source document and the Case Report Form (CRF) detailing circumstances leading to the withdrawal.

Subjects who drop out or are withdrawn will not be re-entered into the study at a later date.

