7.8.4 Use of Data Following Withdrawal

In cases where the subject withdraws consent, the data collected up to the point of withdrawal may be used but no additional data for that subject may be collected.

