8. STUDY DESIGN

8.1 STUDY DESIGN

[figure not shown]
This is a prospective, multicenter study to evaluate the clinical and intraoperative outcomes from 80 subjects implanted with the SUTUREFIX ULTRA and/or SUTUREFIX CURVED Suture Anchors in hip or shoulder groups. Up to 8 sites (up to 4 sites for study hip group and up to 4 sites for study shoulder group) in Europe will participate in the study. Data from eligible subjects, who have provided written and informed consent for the collection of their coded data (see section 9.1.2-9.1.6) will be recorded from the subject medical file on Case Report Forms (CRFs). Follow-up clinical assessments will be performed at 6 months and 1 year post-operatively.

Suturefix Ultra Suture Anchor Suturefix Curved Suture Anchor Prospective, Multicenter, Post-Market 1 year Clinical Follow-up Study to evaluate safety and performance of the SUTUREFIX ULTRA and SUTUREFIX CURVED Suture Anchors in shoulder and hip arthroscopic repair	 Number: 17-5010-06 Version: 1.0, 09/MAY/2018 Page: Page 34 of 87
---	--

This is an open-label study with consecutive enrollment. The study will continue for 12 months from the date of treatment for the last subject completing the study as planned. Only subjects who meet the enrollment criteria as listed in section 7 will be enrolled into the study. The study duration is planned for 24 months.

The data will support CE Mark certification for the Shoulder and Hip repair indications. The data should confirm safety and performance levels acceptable for the risk benefit profile of this device.

Figure 8.1-1: Study Flowchart

Suturefix Ultra Suture Anchor	
Suturefix Curved Suture Anchor	
Prospective, Multicenter, Post-Market 1 year Clinical Follow-up Study to evaluate safety and performance of the SUTUREFIX ULTRA and SUTUREFIX CURVED Suture Anchors in shoulder and hip arthroscopic repair	Number: 17-5010-06
	Version: 1.0, 09/MAY/2018
	Page: Page 35 of 87

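### Read as written, a subject declared lost after missing the 6-month visit is not approached at 12 months, and a later failure has no clear route into the data, although consent stands

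*Combined protocol and SAP*

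**What the plan says.** Four parts of the protocol bear on a subject who misses a visit and cannot be reached.

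- Section 7.7 opens the process with the remark "Some actively enrolled subjects will not return for follow-up exams on time". It asks for a reasonable effort under site policy, with "no fewer than 2 documented phone contacts and 1 certified letter without response". It gives no earliest date for the declaration and does not mention a subject who reappears.
- Section 7.8.2 lists "subject lost to follow-up" among the reasons for which the investigator may withdraw someone. It adds: "Subjects who drop out or are withdrawn will not be re-entered into the study at a later date".
- Section 9.1.8 puts in the discontinued group those "who are lost to follow-up, so are ineligible for further participation", and refers to section 7.8. Its next sentence reads: "Where possible, a full Exit Visit should be completed for all subjects who discontinue the study early".
- Section 7.8.4 limits collection only after consent is withdrawn: "In cases where the subject withdraws consent, the data collected up to the point of withdrawal may be used but no additional data" may be collected for that subject.

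As context, Visit 3 is at 6 months and Visit 4 at 12 months, each with a window of one month either side, and Visit 4 may be a telephone call (section 9.1.5). Section 8.1 has study data transcribed to the CRF from the medical file.

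**The concern.** A lost subject has not withdrawn consent. The implant is permanent and given once, and section 7.8.1 treats withdrawal from treatment as not applicable, so there is no treatment reason to end observation. A subject who ignored the 6-month invitation may still answer a call at month 12, or may come back to the same surgeon because the repair has failed. If the site follows sections 9.1.8 and 7.8.2 literally, it does neither the call nor the recording.

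The stake is possible selective loss. Failure or re-intervention is a plausible reason to reappear, although the documents give no figure for how often that happens. If those who reappear fail more often than those who stayed, leaving them out makes the reported success rate too high. It also removes safety events from a study whose stated purpose (section 4.3) is post-market evidence on safety and performance at 6 and 12 months.

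**Working it through.** **The plan's own figure.** Section 11 gives 40 subjects, 89% success and a 95% interval of 78 to 100 with 55% probability. For X ~ Bin(40, 0.89), the probability that the two-sided Clopper-Pearson 95% interval has half-width at most 0.11 is 0.547. The figure reproduces and is not in dispute. Section 11 states no allowance for dropout.

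**Timing.** The Visit 3 window closes at 6 + 1 = month 7. The Visit 4 window runs from 12 − 1 = 11 to 12 + 1 = month 13. A declaration at about month 7 is therefore permitted four months before the 12-month window opens and six months before it closes.

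**Routes by which a month-9 failure could still enter the data.**

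- Exit Visit (9.1.8): requested for early discontinuations if it can be done. Table 9.1.1-1 shows the exit procedure only at Visit 4, and no text opens it to a lost subject who returns months later or lets it stand as the 12-month assessment.
- Unscheduled examination (9.1.6): at the investigator's discretion, with CRF entry. Nothing says whether it covers a subject already classed as discontinued.
- Adverse events: section 12.1.1 defines them up to study discontinuation, and section 4.4 ends follow-up of unresolved events at loss to follow-up. Sections 12.4 and 12.4.1 cover events already ongoing at discontinuation, not a repair that fails later.
- Medical file: not forbidden by 7.8.4, but no section requires it to be searched for lost subjects.

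Each route is partial or undefined.

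**Size per omitted failure.** The documents give no loss rate, so these inputs are assumptions: 40 subjects in a joint group, 4 declared lost, 33 successes among the other n = 36, and analysis of observed cases. If k lost subjects are recovered and d of them failed,

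excess = 33/36 − (33 + k − d)/(36 + k).

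| Recovered k | Failed d | Rate with them included | Excess in reported 91.7% |
|---|---|---|---|
| 1 | 1 | 33/37 = 89.2% | 2.5 points |
| 2 | 2 | 33/38 = 86.8% | 4.8 points |
| 4 | 4 | 33/40 = 82.5% | 9.2 points |
| 1 | 0 | 34/37 = 91.9% | −0.2 points |
| 4 | 0 | 37/40 = 92.5% | −0.8 points |

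The step per failure falls from 2.5 points (36 to 37 subjects) to 33/39 − 33/40 = 2.1 points (39 to 40). The excess is positive only if those left out fail more often than the 3/36 = 8.3% seen in the rest.

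**Sensitivity at the planning rate.** With 89% success among those observed and 4 of 40 lost, the rate over all 40 is (36 × 0.89 + 4 × 0.78)/40 = 87.9% if the lost fail at 22%, and (36 × 0.89 + 4 × 0.50)/40 = 85.1% if they fail at 50%. The excess is 1.1 or 3.9 points. With 2 to 8 lost, it runs from 0.55 to 2.2 points at 22%, and from 1.95 to 7.8 points at 50%. These figures suppose that every lost subject could be recovered, so in each scenario they are upper limits on what the rule costs. Precision hardly changes: the Wald half-width goes from 9.7 points at n = 40 to 10.2 at n = 36.

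**The case against.** The strongest reply is that the bar is inferred. No sentence forbids the 12-month call or an unscheduled-visit CRF by name. Section 7.7 sets a minimum of effort and does not tell a site to declare loss at month 7, and a missed visit alone is not enough. Withdrawal under 7.8.2 is discretionary, and its re-entry sentence does not name lost subjects. The clause in 9.1.8 could be taken as a loosely worded description of status, and the next sentence asks for an Exit Visit. All this stands as a limit on the claim. It does not remove it: 9.1.8 is categorical, nothing provides for the subject who reappears, and a site that follows the text would stop.

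Two stronger readings are tempting. A reader might infer that the protocol prohibits any further data from lost subjects. It does not: the only explicit prohibition, in 7.8.4, concerns withdrawn consent. A reader might also take 82.5% as the size of the bias. That needs all four lost subjects to have failed and all four to be recoverable after ignoring two calls and a certified letter. Failures in subjects who would never resurface are ordinary missing data, not a product of this rule.

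The observed-case denominator is also assumed. The rule in section 10.3 that bases percentages on non-missing values is written for baseline data.

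**Conclusion.** The point holds as a conflict between a stated rule and the data the study needs. Sections 7.7, 7.8.2 and 9.1.8 together permit an early declaration of loss that, read as written, ends contact with a consenting subject before the 12-month assessment, and the remaining routes are undefined.

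The effect falls mainly on 12-month clinical success, device-related re-intervention, time to failure (10.4.3) and safety. A reader might infer that the primary endpoint is compromised. The documents support that only where later contact or the file would supply the missing 6-month status, for example a re-intervention before month 6 that came to light afterwards.

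The total size is unknown. Each recoverable failure left out is worth roughly 2 to 2.5 points with 36 to 40 evaluable subjects per joint, given an observed-case analysis. An upward bias also requires that the subjects left out fail more often than those retained, which is plausible but not shown. The study is exploratory and unpowered (8.4), so no test result depends on this; the estimates and the safety record do.

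**What to change.** 1. In 7.7, treat a missed Visit 3 as a missed visit. Attempt the 12-month contact in every subject who has not withdrawn consent, and declare loss to follow-up only when the 12-month window closes.
2. In 9.1.8, delete the ineligibility clause for lost subjects.
3. In 7.8.2, state that the re-entry bar does not apply to subjects who were only lost to follow-up. Leave it unchanged for all other withdrawals: limiting it to withdrawal of consent would also reopen participation for subjects withdrawn for noncompliance, adverse events or a sponsor decision, which this point does not justify.
4. For subjects not reached, and where consent covers it, record failure and re-intervention status at 6 and 12 months from the site's medical file. The consent form was not available for this review, so that condition needs checking.

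The cost is protocol wording, one further contact attempt for each missed subject and a look in a file the site already holds. A few subjects stay open until month 13, which is already the end of the Visit 4 window.

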9.1.9 Subject Pregnancy

Women of child-bearing potential are not excluded from the study as long as adequate birth control methods are being used by the subject as outlined in the protocol's exclusion criteria. However, if a woman becomes pregnant during the study, S&N must be contacted immediately once the investigator is made aware of the pregnancy and a decision will be made regarding the continuation in the study of the pregnant woman. Pregnancy is not an adverse event; however, complications related to the pregnancy may be reportable as determined on a case-by-case basis. Pregnancy-related information will be collected until the end of the pregnancy.

9.2 STUDY METHODS AND MEASUREMENTS

All subjects

- VAS for pain and satisfaction assessment*

Hip subjects

- Hip Outcome Score Activities of Daily Living (HOOS-ADL)*
- Modified Harris Hip Score (HHS) *

Shoulder subjects

- ROWE Shoulder Scores*
- ASES Shoulder Scores*
- Constant-Murley Shoulder Scores*

**Patient Reported Outcomes (PROs) are optional and used according to the surgeon's preference*

9.3 HEALTH ECONOMICS/QUALITY OF LIFE

- EQ-5D-5L

10. STATISTICAL DESIGN

The primary aim of the study is to evaluate intra-operative (6 and 12-month) safety and performance of the SUTUREFIX ULTRA and SUTUREFIX CURVED Suture Anchors for arthroscopic repair. This section of the protocol is a brief description of the analyses projected to

Study Protocol—Device	
Prospective, Multicenter, Post-Market Clinical Follow-up Study to evaluate safety and performance of the SUTUREFIX ULTRA and SUTUREFIX CURVED Suture Anchors in shoulder and hip arthroscopic repair	Number: 17-5010-06
	Version: 1.0, 09/MAY/2018
	Page: Page 45 of 87

evaluate the aims of the study and answering the study research question. A more detailed Statistical Analysis Plan (SAP) will be written and finalized prior to database lock. The SAP will account for any changes or deviations from the projected analyses in this protocol.

10.1 GENERAL

Primary and secondary endpoints will be evaluated using listings and appropriate summary statistics. The outcomes will be summarized for the entire sample, by device implanted (SUTUREFIX ULTRA and SUTUREFIX CURVED) as well as the position, i.e. the hip or the shoulder. The summary statistics for both primary and secondary outcomes will be reported together with a 95% confidence interval where necessary to assess the degree of precision in the estimates.

Data tabulations and summarization will be presented to aid in the interpretation of the effects of clinically important variables that are disclosed. A summary of the enrolment figures by site, time point follow-up as well as the demographic and baseline variables, which include age, gender etc. will be presented. Continuous variables will be summarized using mean, median, SD, minimum, and maximum; categorical variables will be summarized as counts and percentages.

All statistical tests will be exploratory in nature as the study is not powered for any statistical testing. Appropriate parametric and/or non-parametric analyses will be chosen for statistical analysis. Test of association for the table of counts will be based on the Fisher's Exact Test unless otherwise inappropriate. The exploratory analysis of continuous variables will be done using t-test and ANOVA if appropriate. The Wilcoxon rank-sum or Kruskal-Wallis tests will be explored if the data is non-normal.

For the success/failure variable, the logistic model will be considered if needed. Associated factors will be adjusted for in unadjusted and adjusted models, if necessary (Peacock and Kerry 2007).²⁵ All statistical tests and models will be considered at 5% significance level. Adverse Events will be tabulated for the study duration.

Study Protocol—Device	
Prospective, Multicenter, Post-Market Clinical Follow-up Study to evaluate safety and performance of the SUTUREFIX ULTRA and SUTUREFIX CURVED Suture Anchors in shoulder and hip arthroscopic repair	Number: 17-5010-06
	Version: 1.0, 09/MAY/2018
	Page: Page 46 of 87

All statistical analyses and calculation of confidence intervals will be performed using SAS software.

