4.3 STUDY PURPOSE

This is a prospective, multicenter study to evaluate intra-operative, 6 and 12-month safety and performance of the SUTUREFIX ULTRA and SUTUREFIX CURVED Suture Anchors for arthroscopic soft tissue repair to meet PMCF requirements for CE Mark and Notified Body (BSI) when used for any of the following indications:

Hip

- Acetabular labrum repair/reconstruction

Shoulder

- Capsular stabilization
 - Bankart repair
 - Anterior shoulder instability
 - SLAP lesion repairs
 - Capsular shift or capsulolabral reconstructions
- Rotator cuff tear repairs
- Biceps tenodesis
- Acromioclavicular separation repairs
- Deltoid repairs

Suturefix Ultra Suture Anchor Suturefix Curved Suture Anchor Prospective, Multicenter, Post-Market 1 year Clinical Follow-up Study to evaluate safety and performance of the SUTUREFIX ULTRA and SUTUREFIX CURVED Suture Anchors in shoulder and hip arthroscopic repair	 Number: 17-5010-06 Version: 1.0, 09/MAY/2018 Page: Page 21 of 87
---	--

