5. OBJECTIVE(S)

5.1 PRIMARY OBJECTIVE

The purpose of this study is to demonstrate the safety and performance of the SUTUREFIX ULTRA and SUTUREFIX CURVED Suture Anchors in hip and shoulder arthroscopic repair over a time period of 12 months after arthroscopy.

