8.3.2 Secondary Endpoints

- Clinical success rate, defined as subjects without signs of failure and/or re-intervention at 12 months, as assessed by the surgeon
- Intra-operative anchor deployment success rate
- Number of anchors pulled out
- Use of additional anchors as a result of intra-operative failure
- Device-related re-intervention
- Safety evaluation at all time points
- Post-operative clinical success rate and performance assessed with subject reported outcomes as follows:

All subjects:

- Subject pain assessment with VAS at 6 months* and 12 months*
- Subject satisfaction assessment with VAS at 6 months* and 12 months*
- EQ-5D Questionnaire at 6 months* and 12 months*

Suturefix Ultra Suture Anchor Suturefix Curved Suture Anchor	
Prospective, Multicenter, Post-Market 1 year Clinical Follow-up Study to evaluate safety and performance of the SUTUREFIX ULTRA and SUTUREFIX CURVED Suture Anchors in shoulder and hip arthroscopic repair	Number: 17-5010-06 Version: 1.0, 09/MAY/2018 Page: Page 36 of 87

Hip subjects:

- Hip Outcome Score Activities of Daily Living (HOOS-ADL) at 6 months* and 12 months*
- Modified Harris Hip Score (HHS) at 6 months* and 12 months*

Shoulder subjects:

- ROWE Shoulder Scores at 6 months* and 12 months*
- ASES Shoulder Scores at 6 months* and 12 months*
- Constant-Murley Shoulder Scores at 6 months* and 12 months*

** Patient Reported Outcomes (PROs) are optional and used according to the surgeon's preference*

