9.1.2 Visit 1: Pre-Operative Visit

- Obtain written informed consent from the subject as detailed in Section 7.5
----- Do not proceed until consent has been obtained -----
- Obtain demographic information and medical history, including information on all concomitant medications/therapies
- Screen the subject for protocol inclusion/exclusion criteria
- Assign the subject a study number and instruct the subject on treatment procedures
- Complete Screening and Enrollment Log
- Complete VAS-Scale for Pain for all subjects*
- Complete EQ-5D questionnaire for all subjects*
- Complete ROWE Score for shoulder*
- ASES Score for shoulder*
- Complete Constant-Murley Score for shoulder*
- Complete HOOS-ADE Score for hip*
- Complete Modified HSS Score for hip*
- Perform MRI, only in case of repair failure
- If any adverse events are observed or reported, they must be recorded as instructed in Section 12.3, adverse events and device deficiencies
- Complete Pre-Operative Visit CRFs

**Patient Reported Outcomes (PROs) are optional and used according to the surgeon's preference.*

Study Protocol—Device	 smith&nephew
Prospective, Multicenter, Post-Market Clinical Follow-up Study to evaluate safety and performance of the SUTUREFIX ULTRA and SUTUREFIX CURVED Suture Anchors in shoulder and hip arthroscopic repair	Number: 17-5010-06
	Version: 1.0, 09/MAY/2018
	Page: Page 40 of 87

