10.2 ANALYSIS POPULATIONS

All subjects who provide informed consent are considered study participants. Study populations are defined as follows:

- Full analysis set population (FAS), including all subjects who were enrolled into the study and attended at least one post-baseline assessment.
- Per-Protocol Population (PP), including all subjects in the full analysis set who have no significant protocol deviations and met the inclusion/exclusion criteria.
- Safety Population (SAF), including all subjects who have received IP.

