10.5 SAFETY ANALYSES

Adverse events

- Adverse Events (as defined in Safety Reporting Section – All adverse events will be tabulated classified by seriousness and given by frequency and percentages for the entire sample and by device implanted (SUTUREFIX ULTRA and SUTUREFIX CURVED)).

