12.1.1 Adverse Event

An Adverse Event (AE) is any untoward medical occurrence between enrollment (signed ICF obtained) and study discontinuation with the use of an IP, whether or not considered causally related to that IP.

AE is used both to refer to AE which are non-serious non-IP or procedure-related and as an umbrella term referring to adverse events of all classifications.

An AE can be any unfavorable and unintended sign (for example, an abnormal laboratory finding), symptom, or disease. For reporting purposes, emphasis is placed first and foremost on whether or not the event constitutes an untoward medical occurrence.

Study Protocol—Device	
Prospective, Multicenter, Post-Market Clinical Follow-up Study to evaluate safety and performance of the SUTUREFIX ULTRA and SUTUREFIX CURVED Suture Anchors in shoulder and hip arthroscopic repair	Number: 17-5010-06
	Version: 1.0, 09/MAY/2018
	Page: Page 52 of 87

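### At the 6-month and unscheduled visits neither the schedule nor the recording instruction calls for adverse events in general, although sections 4.4 and 12.2 require them

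*Combined protocol and SAP*

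**What the plan says.** The general rules are broad. Section 12.1.1 defines an AE as "any untoward medical occurrence between enrollment (signed ICF obtained) and study discontinuation with the use of an IP", whether or not it is thought to be caused by the product. Section 4.4 obliges the investigator to ask specifically about AEs at every contact. Section 12.2 has AEs of all kinds entered in the CRF and source notes, and section 21.5 (item 8) repeats the duty to record each one.

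The visit-level instructions are narrower. At Visit 1, section 9.1.2 says "If any adverse events are observed or reported, they must be recorded". Sections 9.1.3 to 9.1.6 (Visit 2, Visit 3, Visit 4 and unscheduled visits) replace adverse events in that trigger with adverse device effects or device deficiencies. All five texts send the reader to section 12.3 and give it the title of section 12 (adverse events and device deficiencies). Section 12.3 actually concerns unblinding and is marked not applicable. The AE row of the schedule, in both the synopsis schematic and Table 9.1.1-1, is ticked at Visits 2 and 4 only.

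On the analysis side, "Safety evaluation at all time points" is a secondary endpoint (8.3.2), and the study purpose is to "evaluate intra-operative, 6 and 12-month safety and performance" (4.3). Section 10.1 states that "Adverse Events will be tabulated for the study duration". Section 10.5 adds that "All adverse events will be tabulated classified by seriousness and given by frequency and percentages for the entire sample" and by device implanted.

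**The concern.** Safety at 6 months is part of the stated purpose, and Visit 3 is the visit at which the primary endpoint is assessed. A coordinator is likely to work from the schedule and the visit checklist, and at Visit 3 neither asks for AEs in general. The checklist asks for device effects, which are AEs that the investigator has already judged related to product or procedure (12.1.2). Followed literally, it makes the relatedness judgement the gateway to recording. An event judged unrelated would then not be in the database for anyone to look at again, and the table of all AEs promised in 10.5 would be incomplete in a way that no later analysis could repair. The wrong cross-reference adds to this, because a reader who follows it does not arrive at the rule that would correct the narrower wording.

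**Working it through.** The plan gives no figure on this point, so the check sets its sections side by side.

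**Step 1: what each visit asks for.** The ticks are read from the tables as extracted; the two copies of the schedule agree.

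| Visit | Trigger in visit text | AE row ticked |
|---|---|---|
| 1, pre-operative (9.1.2) | adverse events | no |
| 2, operation to discharge (9.1.3) | device effects, deficiencies | yes |
| 3, 6 months (9.1.4) | device effects, deficiencies | no |
| 4, 12 months (9.1.5) | device effects, deficiencies | yes |
| Unscheduled (9.1.6) | device effects, deficiencies | no |

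The trigger names adverse events in general at 1 of 5 visit types, and the schedule ticks AE assessment at 2 of 5. Both do so at 0 of 5. Neither does so at 2 of 5: Visit 3 and unscheduled visits. Section 4.4 requires it at 5 of 5.

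**Step 2: which events are exposed.** Under 12.1.2, an AE with a possible, probable or definite relationship to the product or the procedure is a device effect. One that is definitely unrelated, or unlikely to be related, is not. The trigger in 9.1.4 therefore covers the first class and leaves out the second. Serious events of either class must reach the sponsor within 24 hours under 12.2. What is left mainly exposed is the non-serious AE judged unrelated or unlikely to be related.

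**Step 3: whether a later check would recover them.** The sponsor's medical review in 12.2 covers SAEs and ADEs, so a non-serious event judged unrelated would not come before it. By the schedule, the only AE assessment after discharge is at Visit 4, at 12 ± 1 = 11 to 13 months, possibly by telephone. A tick at Visit 3 would put one at 6 ± 1 = 5 to 7 months.

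**Step 4: the cross-reference.** The recording rule is in 12.2. The table of figures numbers the AE reporting figure 12.3-1, while the figure itself is captioned 12.2-1. That points to a subsection number left over from a renumbering: the title cited is right for section 12, but the number is wrong.

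**Step 5: size.** The documents give no expected AE rate and no share of events judged unrelated. The number of events at risk of being missed cannot be computed, and none is offered here.

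**The case against.** The strongest reply is that the binding rule is already clear. Sections 4.4, 12.2 and 21.5 all require AEs to be sought or recorded, and each visit text from Visit 2 onward begins by asking about changes in general health and concomitant medication, which would bring many events to light. The citation of 12.3 carries the words adverse events in its title, so a reader would probably find section 12. All of this stands. It makes the matter a conflict between general rules and visit instructions, not a rule that AEs go unrecorded.

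Four stronger readings are tempting, and the documents do not support them.

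- *The schedule restricts Visit 3 to device effects.* It does not. The row is simply blank; only the visit text draws that distinction.
- *Infection and inflammatory, foreign body or allergic reactions would be lost at 6 months.* Section 4.4 lists these as anticipated device effects, and 12.1.2 counts even a possible relationship to device or procedure. The Visit 3 trigger covers them whenever a relationship is thought possible.
- *The plan has decided to pool AEs over time, leaving the all-time-points endpoint without an analysis.* The sentence in 10.1 can equally be read as stating coverage. Section 10 calls itself a brief description, commits secondary endpoints to listings and summary statistics, and defers detail to a SAP to be finalised before database lock, which is not among the documents. Failure and re-intervention are reported at 6 and 12 months in any case (10.4.1, 10.4.2).
- *Pre-operative events distort the safety percentage.* AEs do run from consent, and the definition "Safety Population (SAF), including all subjects who have received IP" restricts subjects, not events. One implanted subject whose only AE was pre-operative would add 1/80 = 1.25 points. No rate of such events is given, so no distortion can be claimed.

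**Conclusion.** Wrong as written, and minor. At two of five visit types, one of them the 6-month visit, neither the schedule nor the recording trigger calls for AEs in general, against 4.4 and 12.2, and all five visit texts cite the wrong subsection. The consequence is a risk of under-recording, chiefly of non-serious AEs judged unrelated or unlikely to be related to device or procedure. These bear least on device safety, but 10.5 promises to tabulate all AEs, and the judgement that separates them should follow capture.

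The conclusion assumes that the ticks were extracted correctly, which the agreement of the two copies supports, and that some sites work from the visit instructions and not from sections 4.4 and 12.2. The finding on the visit text and the cross-reference does not depend on the table.

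**What to change.** In the protocol:

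1. Tick AE assessment at Visit 3 and at unscheduled visits, in both the synopsis schematic and Table 9.1.1-1.
2. In 9.1.3 to 9.1.6, word the trigger as *adverse events, adverse device effects or device deficiencies*.
3. In 9.1.2 to 9.1.6, change the reference from 12.3 to 12.2.

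These are wording changes. They add no visit and no assessment beyond what 4.4 already requires. If enrolment has begun, they go through the amendment process in section 15.

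A secondary suggestion for the SAP, on which the finding does not depend: summarise AEs in the Safety Population, list events with onset before surgery separately, and give the cumulative number and percentage of subjects with an AE by discharge, by 6 months and by 12 months. That would match the endpoint "Safety evaluation at all time points" and keep the total for the 12-month objective in 5.1. Cumulative counts are preferable to separate counts per period, because a subject can have events in more than one period and the period counts cannot be added to give subjects affected by 6 months. The cost is a few descriptive tables, provided that the CRF records AE onset dates, which the documents do not show.
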